3.6.2 Time to erectile function recovery

This will be defined as the time from surgery to the time of first reaching an IIEF-5 score larger or equal to 15.

3.6.3 Urinary continence recovery

Urinary continence recovery (binary outcome) will be defined at each time-point, based on whether the ICIQ score is less or equal to 5.

3.6.4 Time to urinary continence recovery

This will be defined as the time from surgery to the time of first reaching a ICIQ score of 5 or below.

3.6.5 Oncological outcome

Oncological outcome after 12 months (categorical outcome) will be classified into four categories according to the following definition:

1. PSA persistence
PSA \geq 0.2 at visit 2
2. Biochemical recurrence
PSA $<$ 0.2 at visit 2
AND
(PSA \geq 0.2 at visit 3 **OR** PSA \geq 0.2 at visit 4)
3. Early salvage treatment
PSA $<$ 0.2 at each of visit 2, visit 3, and visit 4

AND

Received adjuvant treatment* in the first year

4. Other (No recurrence or treatment)

PSA<0.2 at each of visit 2, visit 3, and visit 4

AND

No adjuvant treatment* in the first year

*Adjuvant treatment is defined as any adjuvant cancer treatment during the first year after surgery, as recorded on the study questionnaire at visit2, visit3 and visit4, under the question “Did the subject have any or have any adjuvant therapy planned?”. Common adjuvant treatment could include Hormonal Treatment or Radiotherapy.

Handling of partially missing information for oncological outcome

Participants with no adjuvant treatment reported will be considered as not receiving adjuvant treatment. Missing treatment date will be handled as discussed above (see section 3.3).

Participants with undefined oncological status due to missing PSA values will be reviewed case by case. If a participant has a PSA below 0.2 at a visit and has not started treatment since, we will assume previous PSA values were below 0.2. We will also use the later available PSA values (visit 5, part of the longer-term follow-up) to apply this rule.

For patients who died during the 12 months follow-up, we will report their oncological status before death (if available) but indicating that these patients have died, with the reason of death.

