	
Comparison of the proportion of men with BCR between NeuroSAFE and control arms within 12 months of surgery. BCR will be considered to have occurred when the post operative PSA measures <math>>0.2\text{ng/mL}</math>, or where the PSA level is less than <math>0.2\text{ ng/mL}</math> but the trajectory suggests inevitable rise above <math>0.2\text{ ng/mL}</math> according to the clinician looking after the patient. If PSA fails to nadir after surgery, this will not be considered BCR as this is probably related to micro metastatic disease not detected by preoperative imaging.
 
For further descriptive analyses, sub-group analyses, and sensitivity analyses please see body of protocol, Outcomes Section.
 
3) Additional oncological treatments
 
 
‘Adjuvant treatment’ refers to men who undergo additional cancer treatment without having BCR. A descriptive analysis of the proportion of men undergoing adjuvant oncological treatments (ADT and/or radiotherapy and/or chemotherapy) at or before 12 months of surgery will be conducted.
 
‘Salvage treatment’ refers to men who undergo additional cancer treatment following BCR. A descriptive analysis of the proportion of men undergoing adjuvant oncological treatments (ADT and/or radiotherapy and/or chemotherapy) at or before 12 months of surgery will be conducted.
 
 
4) Quality of Life
 
 
A comparison of the proportion of men achieving the best quality of life according to the EQ-5D-5L between intervention and control arms.
 
Analysis of EQ-5D-5L scores to produce QALYs at 12 months by arm
 
Analysis of RAND36 scores to produce QALYs at 12 months by arm
 
Analysis of EPIC-26 scores at 36, 48 and 60 months after surgery and a maximum frequency of annually thereafter
 
 
5) Positive Surgical Margins (PSM)

--	--

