#### Verbal questionnaire responses (telephone)

- Since the Covid-19 Pandemic and government restrictions on movement including hospital appointments, the NeuroSAFE PROOF team have been conducting trial follow-up visits via telephone. All trial questionnaires have been sent to participants in the post. In order maintain data completeness on key outcome measures (such as erectile function at 12-months [IIEF-15] and urinary continence at 3 months [ICIQ]), the trial clinical team have been administering these PROM questionnaires over the telephone.

- As of protocol version 5.0, to ensure data completeness and to avoid submitting repeated protocol deviations for each instance, this method of data capture is now an accepted method of data collection. Any paper copies returned by post will supersede verbal responses.
- In order to distinguish between source data origins, a new electronic CRF database will have the facility to record whether PROM items were obtained by paper questionnaires submitted by post, electronic versions submitted following email reminders, or verbally with a clinician over the telephone.

Further planned analyses:

- Additional subgroup analysis: restricted to men who did not receive a pre-operative radiologist recommendation for bilateral nerve sparing.
- Additional subgroup analysis: patients who did not receive adjuvant treatment (adjuvant therapy defined as any additional treatment without a  $PSA > 0.2 \text{ ng/ml}$ ).
- Sensitivity analyses: additional analysis at 12 months
  - (a) IIEF-5 using a threshold  $\geq 15$
  - (b) IIEF-5 using a threshold of  $\geq 2$  for question 3
- Descriptive analysis of IIEF-5 at 3-, 6-, 12- and 24-months post-surgery

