#### 7.2.2.3. Additional oncological treatments

For men who receive additional cancer treatment, despite not having reached a PSA threshold of  $PSA > 0.2$  ng/ml post-surgery will be considered as having undergone 'adjuvant treatment.' Descriptive analysis of proportions of men undergoing adjuvant oncological treatments at or before 12 months of surgery, including tabulating the types of treatment that these men underwent. Reasons for adjuvant treatment (i.e. before BCR) will be documented where possible.

Men who receive additional cancer treatment, following a PSA at or above the threshold of  $PSA > 0.2$  ng/ml post-surgery will be considered as having undergone 'salvage treatment.' Descriptive analysis of proportions of men undergoing salvage oncological treatments at or before 12 months of surgery, including tabulating the types of salvage treatment that these men underwent.

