4.9.4 Oncological outcome

We will report descriptively the oncological outcome during the first year, presenting the frequency and percentage in each category, by arm.

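### The SAP's early-salvage category does not match either protocol definition of salvage, and the planned table cannot give the 12-month adjuvant and salvage proportions the protocol asks for

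*SAP*

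**What the plan says.** **Protocol 7.2.2.3** defines two groups by a PSA threshold of 0.2 ng/ml.
- Adjuvant: "For men who receive additional cancer treatment, despite not having reached a PSA threshold of" more than 0.2.
- Salvage: "Men who receive additional cancer treatment, following a PSA at or above the threshold of" more than 0.2.

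It asks for the 12-month proportion of each, with treatment types tabulated. For salvage: "Descriptive analysis of proportions of men undergoing salvage oncological treatments at or before 12 months of surgery". The threshold definition of adjuvant recurs in the subgroup lists of 7.2.1 and 7.2.2.1: "patients who did not receive adjuvant treatment (adjuvant therapy defined as any additional treatment without a" PSA above 0.2.

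**Protocol section 2 (Trial Overview)** defines the same terms through biochemical recurrence (BCR). Adjuvant "refers to men who undergo additional cancer treatment without having BCR"; salvage "refers to men who undergo additional cancer treatment following BCR". Section 2 and 7.2.2.2 let the treating clinician declare BCR below 0.2 on the PSA trajectory. They also say that failure to reach a nadir is not BCR.

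**SAP 3.6.5** defines one four-level variable:
1. PSA persistence: 0.2 or more at visit 2.
2. Biochemical recurrence: below 0.2 at visit 2, then 0.2 or more at visit 3 or 4.
3. "3. Early salvage treatment": below 0.2 at all three visits, and treated in the first year. The criterion itself calls the treatment adjuvant.
4. Other: below 0.2 at all three visits, and untreated.

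**SAP 4.9.4** reports this variable by "presenting the frequency and percentage in each category, by arm". SAP 1.2.2 keeps 12-month oncological outcomes in scope; it marks only quality of life and economics as not covered.

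**The concern.** There are two defects.

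First, a reader comparing arms would naturally take the row named salvage as the protocol's salvage rate. It is a group with no visit PSA of 0.2 or more.

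Second, treatment enters the SAP variable only after PSA failure has been ruled out. Treated and untreated men with persistence or recurrence are pooled, so the table does not show who among the PSA failures went on to further treatment.

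This matters because the need for further treatment, chiefly radiotherapy, is part of the trial's rationale (protocol 3.1 and 4.4). Protocol 6.2 also names adjuvant and salvage treatment among the 12-month oncological outcomes to be compared.

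**Working it through.** The documents give no adjuvant or salvage rate, so there is no figure to reproduce. The check is whether the SAP categories map onto the protocol groups.

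**Step 1. Treated men, side by side.** This takes a PSA of 0.2 or more at visit 2 as the protocol's failure to reach a nadir.

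| Treated man | SAP 3.6.5 | Protocol 7.2.2.3 | Protocol section 2 and 7.2.2.2 |
|---|---|---|---|
| Below 0.2 throughout, no concern about trajectory | 3 | Adjuvant | Adjuvant |
| Below 0.2 throughout, treated on a rising trajectory judged to be BCR | 3 | Adjuvant | Salvage |
| Above 0.2 at visit 2, then treated | 1 | Salvage | Not BCR, so not salvage |
| Below 0.2 at visit 2, above 0.2 at visit 3, then treated | 2 | Salvage | Salvage |
| Treated while below 0.2, above 0.2 at a later visit | 2 | Adjuvant | Adjuvant, unless BCR had been declared on trajectory |

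Category 3 is adjuvant under 7.2.2.3 and mixed under section 2. The salvage label covers all of it under neither.

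**Step 2. All patterns.** Take PSA of 0.1, 0.2 or 0.3 at each of three visits (3 × 3 × 3 = 27). Cross these with five treatment timings: none, before visit 2, between visits 2 and 3, between visits 3 and 4, after visit 4. That gives 27 × 5 = 135 patterns. Class each by SAP 3.6.5 and by 7.2.2.3, with salvage meaning a visit PSA above 0.2 before treatment.

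| SAP category | Untreated | Adjuvant | Salvage | Total |
|---|---|---|---|---|
| 1 | 18 | 37 | 35 | 90 |
| 2 | 8 | 24 | 8 | 40 |
| 3 | 0 | 4 | 0 | 4 |
| 4 | 1 | 0 | 0 | 1 |

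These are logical patterns, not patients or expected frequencies. Every salvage pattern is in category 1 or 2, where it is mixed with untreated and adjuvant patterns. Dropping treatment after visit 4 (27 × 4 = 108 patterns), or counting a PSA of exactly 0.2 as reaching the threshold, changes the cell counts. It does not change that result, and category 3 stays wholly adjuvant.

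**Step 3. What the four counts determine.** Let n1 to n4 be the category counts in one arm.

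| Quantity | Under 7.2.2.3 | Under section 2 |
|---|---|---|
| Salvage | 0 to n1 + n2 | 0 to n2 + n3 |
| Adjuvant | n3 to n1 + n2 + n3 | 0 to n1 + n2 + n3 |
| Any treatment | n3 to n1 + n2 + n3 | n3 to n1 + n2 + n3 |

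None of the three is fixed by the planned table.

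**Step 4. Illustrative size, on assumed rates.** SAP 1.4 gives 202 men per arm. Suppose 5% to 15% fall in categories 1 and 2: 202 × 0.05 = 10 and 202 × 0.15 = 30 men. The salvage count under 7.2.2.3 could then be 0 to 10, or 0 to 30. If 60% to 90% of them are treated, 202 × 0.05 × 0.60 = 6 and 202 × 0.15 × 0.90 = 27 treated men per arm would not be distinguished from untreated men in the same category. The documents support none of these percentages.

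**The case against.** **The label may be deliberate.** A man treated because his PSA is rising below 0.2 can be BCR under 7.2.2.2 and hence salvage under section 2. Early salvage is a fair name for him. This stands in part. A reader might infer that the SAP has simply swapped the names and that category 3 is purely adjuvant; with two unreconciled protocol definitions, the documents do not support that. But category 3 has no trajectory or clinician-judgement condition and also admits men treated with no PSA rise, so the name still does not cover the category.

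**SAP 4.6 promises summaries of all study variables by arm.** This also stands in part. A reader might infer that treated men with PSA failure would appear nowhere as treated. That is too strong, since a raw treatment count by arm falls within 4.6, probably in an appendix. It would not cross treatment with PSA status, and the underlying question does not separate adjuvant from salvage and also captures planned therapy.

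**SAP 3.3 says all available PSA data are used.** A man with PSA 0.3 at a 9-month test who is treated and is below 0.2 at visit 4 meets category 3 only if 3.6.5 is read literally. The two sections leave his class ambiguous. The point does not rest on him.

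**The 30% for adjuvant therapies in protocol 13.7.** A reader might take it as the likely size of the missing group. It is an expected longer-term outcome of surgery, not a 12-month, by-arm or salvage figure.

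**The outcome is descriptive, the criteria are printed, and SAP 2.1 allows further justified analyses.** All true, and this limits the severity. It does not supply two proportions that the protocol pre-specified.

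**Conclusion.** The point holds, at moderate weight. The name of category 3 fits the whole category under neither protocol definition, and the four counts in SAP 4.9.4 do not yield the 12-month adjuvant or salvage proportions of protocol 7.2.2.3. Those outcomes are in the SAP's scope and are not deferred to another plan.

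No test, significance level, power or primary estimand is affected. The consequence is a row open to misreading and a missing pre-specified description. Its size cannot be taken from the documents; the counts in Step 4 rest wholly on assumed rates.

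A reader might also infer that the remedy is to call category 3 adjuvant and all treated men in categories 1 and 2 salvage. The documents do not support that. It would misclass trajectory-based BCR and treated persistence under section 2, and men treated before their PSA reached the threshold under 7.2.2.3.

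**What to change.** 1. **Reconcile the definitions.** Align protocol section 2, 7.2.2.2 and 7.2.2.3, and state in SAP 3.6.5 which meaning of adjuvant and salvage applies. Cover treated PSA persistence, BCR declared on trajectory, and a PSA of exactly 0.2 (the SAP uses 0.2 or more; the protocol's threshold is above 0.2). Section 2's analysis sentence for salvage says adjuvant, apparently a copying slip, and should be corrected.
2. **Rename category 3 neutrally**, for example: Additional treatment with PSA below 0.2 at all visits.
3. **Add one table to SAP 4.9.4, by arm.** Tabulate any additional cancer treatment within 12 months (yes or no, and type) by PSA status (persistence, recurrence, neither). Class treatment as before or after the first PSA at or above the threshold, using all recorded PSA values and treatment dates, and say how treatment that was only planned is handled. Report the adjuvant, salvage and total proportions from this table.

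The cost is some SAP wording and a few table rows. PSA and treatment are already collected at visits 2 to 4 (SAP 3.1), and SAP 3.3 already has rules for missing PSA and treatment dates. No new data collection is needed.

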#### 7.2.2.2. BCR

Comparison of the proportion of men with BCR between NeuroSAFE and control arms within 12 months of surgery. BCR will be considered to have occurred when the post operative PSA measures  $>0.2$  ng/mL, or where the PSA level is less than 0.2 ng/mL but the trajectory suggests inevitable rise above 0.2 ng/mL according to the clinician looking after the patient. If PSA fails to nadir after surgery, this will not be considered BCR as this is probably related to micro metastatic disease not detected by preoperative imaging. Patients with demonstration of metastases on imaging will not be considered as BCR for the same reason.

- Follow up time of 12 months is defined as cumulative time up to the 12-month visit. Patients visits after more than 13.5 months post-surgery will not be included (12 months + 6 weeks max visit window).
- Additional descriptive analysis will report recurrences across all patients at the following times: Within 3 months (+/- visit window) and within 6 months (+/- visit window).
- Descriptive analysis of BCR for each arm according to
  - (a) Gleason grade
  - (b) TNM stage
  - (c) pre-operative PSA level
  - (d) routinely used risk classifiers (D'Amico, CAPRA, EAU) (e) time of recurrence.

If patients have a low but detectable PSA level the frequency of testing would be increased from the usual schedule (3,6,9,12 months) depending on the trajectory and level of concern of the clinician looking after the patient.

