3.3 Time points and dates

Data were aimed to be collected at baseline, 3 months after surgery (visit2), 6 months after surgery (visit3) and 12 months after surgery (visit4).

Outcomes were not always collected at the exact time point, particularly during the COVID-19 pandemic, and we allow some flexibility around the due date to determine if data could contribute to the analysis. Assessments were considered valid if they were collected within the following time windows:

- Visit 2 (3months): Recorded as visit 2, and conducted between 1 to 6 months after surgery
- Visit 3 (6 months): Recorded as visit 3, and conducted between 4 to 12 months after surgery
- Visit 4 (12-months): Recorded as visit 4, and conducted between 9 to 18 months after surgery

Date of PSA measurement available could vary more, and no specific window was applied. All available PSA data were used to determine the oncological outcome to maximally capture any cases of oncological failure.

Handling of missing visit dates:

If the questionnaire date was missing (for IIEF and ICIQ), we will look at the corresponding date for the other questionnaires. If the date of the other questionnaires were also missing, we will impute the date assuming the observation was recorded at the expected time point from surgery.

If the PSA date was missing, we will assume the observation was recorded at the expected time point from surgery.

Treatment date was recorded as day, month, year. If the day was missing, we will assume it was done on the 15th of the month. If the month or full date was missing, we will assume treatment has started on the expected visit date, checking this is consistent with the PSA and other information available.

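### SAP 3.6.5 classifies the 12-month oncological outcome by visit label, not by PSA date relative to treatment, so it can disagree with the protocol's BCR definition in two directions

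*SAP*

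**What the plan says.** SAP section 3.6.5 defines four categories:

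- PSA persistence: PSA at or above 0.2 at visit 2.
- Biochemical recurrence: below 0.2 at visit 2, then at or above 0.2 at visit 3 or visit 4.
- Early salvage treatment: below 0.2 "at each of visit 2, visit 3, and visit 4", with treatment recorded in the first year.
- Other: the same PSA pattern without treatment.

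SAP section 3.3 says of PSA dates: "Date of PSA measurement available could vary more, and no specific window was applied". It continues: "All available PSA data were used to determine the oncological outcome to maximally capture any cases of oncological failure". SAP section 4.9.4 reports the four categories for the first year as counts and percentages by arm, without a test.

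Protocol section 7.2.2.2 counts BCR cumulatively to the 12-month visit and sets an upper limit: "Patients visits after more than 13.5 months post-surgery will not be included". For a low but detectable PSA it says "the frequency of testing would be increased from the usual schedule (3,6,9,12 months", the list ending there. Protocol section 7.2.2.3 calls treatment after the PSA threshold 'salvage' and treatment without reaching it 'adjuvant'. The Trial Overview (section 2) ties salvage to a preceding BCR.

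**The concern.** Three statements do not fit together. SAP 3.3 says all PSA data are used. SAP 3.6.5 has no place for a value that is not labelled visit 2, 3 or 4. The protocol's definition runs on cumulative time with a date limit that the SAP does not carry over. SAP 3.6.5 also looks only at whether treatment was given, so a low PSA that may result from treatment is read as evidence that there was no recurrence.

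Equal cure is one of the three hypotheses in Protocol section 5.1, and BCR is a named secondary endpoint. This table is where the SAP reports 12-month recurrence. Because it is not tested, readers will compare its counts directly, so the rows need to mean what the protocol says they mean.

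**Working it through.** **1. The protocol's limit.** Inputs: 12 months and a 6-week window (Protocol 7.2.2.2 and 7.4). With four-week months, 12 + 6/4 = 13.5 months, which reproduces the stated figure. On the calendar, 12 + 42/30.44 = 13.4 months. The difference is immaterial here.

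**2. The two rules.**

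- SAP 3.6.5, read literally: visit 2 ≥ 0.2 gives persistence; otherwise visit 3 or visit 4 ≥ 0.2 gives BCR; otherwise treatment in year 1 gives early salvage; otherwise other.
- Protocol 7.2.2.2, PSA part: after PSA has fallen following surgery, any value > 0.2 at or before 13.5 months gives BCR.

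The SAP uses at or above 0.2 and the protocol uses above 0.2. No value below equals 0.2, so this difference does not drive the results.

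**3. Invented PSA series put through both rules.**

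| Case | PSA course | SAP 3.6.5 | Protocol |
|---|---|---|---|
| A | 0.03 at 3 months, 0.08 at 6, 0.30 at 9, treated, 0.05 at visit 4 | Early salvage | BCR |
| B | As A, but 0.25 at visit 4 | BCR | BCR |
| C | 0.30 at 9 months, untreated, 0.40 at visit 4 | BCR | BCR |
| D | 0.03 at 3 months, 0.05 at 6, 0.25 at a visit 4 drawn at 16 months | BCR | Not counted |
| E | As A, but the 9-month value is entered as visit 3 | BCR | BCR |

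**4. What the cases show.** Case A needs three things together: PSA first reaches 0.2 between visits 3 and 4, it is below 0.2 again at visit 4 after treatment, and the interim value carries no visit 3 or 4 label. B, C and E each break one condition, and the rules then agree. Between A and E the 9-month result is the same; only its label decides the row. Case D needs only a late visit 4 sample and no earlier raised value.

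**5. Effect on the table.** Count the first three categories as failures. Case A moves a man from row 2 to row 3, so total failures change by 0. Case D, if untreated, moves a man from row 4 to row 2, so total failures change by +1.

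**6. Number of men.** For case A the number per arm is N × b × f, where b is the 12-month BCR proportion and f is the share of those men meeting all three conditions. The documents give neither b nor f. Purely as an assumption, with N = 182 (half of the 364 evaluable men in SAP 1.4, a figure set for erectile function), b = 8% to 15% and f = 0 to 30%, the range is 0 to 182 × 0.15 × 0.30 = 8.2 men. This is an illustration, not an estimate. For case D the documents do not say how many visit 4 samples fell after 13.5 months.

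**The case against.** The case for leaving the rule alone has several parts.

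- **All PSA data are said to be used.** SAP 3.3 can be read as bringing interim values in. But 3.6.5 gives no rule for doing so, and its manual review does not reach them: "Participants with undefined oncological status due to missing PSA values will be reviewed case by case". In case A nothing is missing. What stands is that the two sections must be reconciled.
- **A 9-month PSA may not be trial data.** The assessment tables in both documents list post-operative PSA at 3, 6 and 12 months within the first year, not at 9. This stands. A reader might infer that the SAP discards a scheduled trial measurement; the documents show 9 months only as part of the usual testing schedule.
- **The man is still visible.** He appears in the early-salvage row, so total failures do not change. This stands for case A but not for case D.
- **The lack of a window is deliberate**, with a stated reason. That is true, but the resulting table is still presented as first-year outcome, and the protocol's limit is neither kept nor explicitly replaced.
- **The outcome is descriptive**, and Protocol 13.1.1 gives the data monitoring committee its own quarterly review of oncological outcomes. Both are true and limit the consequence, but neither settles what the published rows mean.

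**Conclusion.** SAP 3.6.5 is wrong as written, in a limited way. Followed exactly, it can file a man with PSA at or above 0.2 before treatment as early salvage, and it can count a first raised PSA after 13.5 months as first-year BCR. Both contradict Protocol 7.2.2.2; the first also contradicts 7.2.2.3 and sits badly with SAP 3.3.

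The first error redistributes men between two failure rows. The second can raise the failure total. The number of men affected cannot be derived from the documents and could be close to zero.

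Two stronger readings are not supported. A reader might infer that every recurrence found at 9 months and treated is lost from BCR; cases B and E show that it depends on the visit 4 value and on the label. A reader might also infer that the table favours one arm; nothing in the documents shows that interim testing, prompt treatment or late sampling differs between arms.

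**What to change.** Reconcile Protocol 7.2.2.2, SAP 3.3 and SAP 3.6.5 before unblinding, and classify by date using every PSA in the trial database, including unscheduled values:

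- **Persistence:** first post-operative PSA at or above 0.2, whatever its visit label. Flag those drawn after the visit 2 window.
- **BCR:** first PSA below 0.2, then any later PSA at or above 0.2, either on or before the start of additional treatment or without treatment, up to 13.5 months. A raised value before treatment takes precedence over a later low one.
- **Early treatment:** treatment in the first year with no earlier PSA at or above 0.2. Footnote any man in this row whose PSA reaches 0.2 after treatment, since the SAP currently calls him BCR.
- **Visit 4 PSA after 13.5 months:** keep the SAP's existing inference that a later PSA below 0.2 without treatment implies earlier values below 0.2. Report a first PSA at or above 0.2 after the limit separately, as a late event.
- State how the protocol's clinician-judged trajectory criterion is handled.
- Show the visit-label classification as a sensitivity check.

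The cost is SAP wording, some reprogramming, and slightly different BCR and early-treatment counts. No new data collection is required, though PSA values never entered in the database will remain unseen.

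### Undated plans for adjuvant treatment can be counted as treatment received in the first year, which shifts men between two categories of the 12-month oncological table

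*SAP*

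**What the plan says.** SAP 3.6.5 sorts men into four oncological categories. The first two, PSA persistence and biochemical recurrence, are set by PSA. Categories 3 and 4 both require PSA below 0.2 at visits 2, 3 and 4, and differ only in the treatment condition: "Received adjuvant treatment* in the first year" for category 3 and "No adjuvant treatment* in the first year" for category 4.

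The footnote to that condition reads "Adjuvant treatment is defined as any adjuvant cancer treatment during the first year after surgery, as recorded on the study questionnaire at visit2, visit3 and" visit 4, and names the question used: "Did the subject have any or have any adjuvant therapy planned". A man with no treatment reported is taken as untreated. No rule covers a man for whom a plan is the only thing reported.

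For missing treatment dates, SAP 3.6.5 refers back to SAP 3.3. There a missing day becomes the 15th of the month. For anything less complete, "If the month or full date was missing, we will assume treatment has started on the expected visit date", followed by a safeguard: "checking this is consistent with the PSA and other information available".

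The protocol endpoint (7.2.2.3) is worded in terms of treatment given: "Descriptive analysis of proportions of men undergoing adjuvant oncological treatments at or before 12 months of surgery". SAP 4.9.4 reports the four categories as frequencies and percentages by arm, without a test.

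**The concern.** The category is defined by treatment received, but the item that feeds it does not distinguish treatment given from treatment intended. A plan may well carry no start date, and the missing-date rule then supplies one inside the first year. Two rules that each look harmless combine to turn an undated intention into a treatment event.

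At stake is the split between categories 3 and 4 in the SAP's main 12-month oncological report. The protocol hypothesises equal cure rates in the two arms (5.1) and lists additional oncological treatments among its secondary outcomes (Trial Overview), so readers will look at this table by arm. The surgeon is not blinded (Protocol 9.2), so the frequency of recorded plans could differ between arms, although nothing in the documents shows that it does.

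Treatment status is used a second time. The rule in SAP 3.6.5 that fills in earlier missing PSA values depends on the man not having started treatment, so a plan read as a start could also affect that step.

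**Working it through.** The documents give no figure for planned-only answers, so there is nothing to reproduce. The check applies the stated rules to two hypothetical men and then shows a range of sizes.

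**Inputs.** Category conditions, source question and PSA back-fill: SAP 3.6.5. Missing-date rule and consistency check: SAP 3.3. Expected visit times of 3, 6 and 12 months after surgery: SAP 3.3. Endpoint: Protocol 7.2.2.3. Number of men for scale: 364 evaluable, 182 per arm (SAP 1.4).

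**Applying the rules.** Both men have PSA below 0.2 at visits 2, 3 and 4. At visit 4 treatment is planned but not begun.

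| Step | Man A: no start date recorded | Man B: start recorded at month 14 |
|---|---|---|
| PSA | Category 3 or 4 | Category 3 or 4 |
| Source question | Yes | Yes |
| Date used | Set to the expected visit date, 12 months | 14 months |
| Within the first year? | Yes | No |
| SAP category | 3 | 4 |
| Protocol 7.2.2.3, treated by 12 months? | No | No |

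The SAP and the protocol agree for man B and disagree for man A. The gap is therefore confined to plans or starts without a month or full date. The same happens at visits 2 and 3, where the assumed start is 3 or 6 months, and the plan may later be delayed or dropped.

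**A related case.** SAP 3.3 accepts assessments recorded as visit 4 from 9 to 18 months after surgery. If the treatment question follows that window, an undated entry made at 15 months would be set back to month 12.

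**Can the consistency check separate the two?** Categories 3 and 4 share the same PSA condition at all three visits, so an undelivered plan and a delivered treatment can look the same on PSA. What remains is the other information, for which SAP 3.3 names no source and no criterion.

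**Size, as an assumption.** Let q be the share of men with PSA below 0.2 throughout and an undated plan that was not delivered by 12 months. Men moved from category 4 to category 3 = q × 364:

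- q = 1%: 0.01 × 364 = 3.6, about 4 men
- q = 3%: 0.03 × 364 = 10.9, about 11 men
- q = 5%: 0.05 × 364 = 18.2, about 18 men
- q = 10%: 0.10 × 364 = 36.4, about 36 men

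Per arm of 182 the range is 1.8 to 18.2 men. Category 3 rises and category 4 falls by the same q percentage points. The 364 is the evaluable number from the IIEF-5 power calculation, used here for scale only; it is not the stated denominator of the oncological table.

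**The case against.** The strongest reply is that the definition already excludes mere plans. It speaks of treatment during the first year, category 3 asks for treatment received, and the question is named as the place where the information was recorded, not as a rule that every yes counts. The consistency check is a real safeguard, and the other information could include later visits: Protocol 7.4 schedules an additional treatments assessment at every follow-up visit, including 2 years, and SAP 3.6.5 already draws on visit 5 PSA. SAP 2.4 has missing data queried with the sites, so imputation may apply only to what is left. The documents also do not show the rest of the form, which may have fields that separate given from planned treatment.

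Much of this limits the point without removing it. The intent of the definition is clear, but the SAP gives no step that carries it out for a planned-only answer. The query process in SAP 2.4 does not say how such an answer is coded.

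A reader might infer that every planned treatment, or every start after 12 months, is misclassified. The documents do not support that: treatment dates were recorded, and a dated start after one year fails the first-year condition. A reader might also infer bias between arms from the unblinded surgeon. That is possible but not shown, and unblinded clinicians could differ in treatment given as well as in treatment planned.

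**Conclusion.** The point holds in a narrow form. Followed as written, SAP 3.6.5 and 3.3 allow an undated plan recorded at visits 2 to 4 to count as treatment received, which moves a man from category 4 to category 3 and departs from Protocol 7.2.2.3. The consistency check may catch some cases but cannot be relied on, because it has no criteria and PSA does little to tell the two categories apart.

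The size is unknown. The range of about 4 to 36 men rests wholly on the assumed 1% to 10%, and it would be smaller if the form separates plans from treatment or if sites resolve most undated entries. With complete PSA, categories 1 and 2 are unaffected. The outcome is descriptive, so no primary or secondary test, power or alpha figure changes. This is a minor but worthwhile correction to the by-arm oncological table.

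**What to change.** Amend SAP 3.6.5 and 3.3 as follows.

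- For category 3, require evidence, either a start date or a source record, that treatment started within 12 months of surgery.
- Do not apply the missing-date rule of SAP 3.3 to planned-only answers. Query them with the site under SAP 2.4.
- Report men with treatment planned but not confirmed as started by 12 months as a separate line, by arm.
- Use the same started or not-started status in the rule that fills in missing PSA values.

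The cost is a few sentences in the SAP, some data queries, and probably a small group whose treatment status stays unconfirmed. No new data collection from patients is needed.
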